#### 5.2.5.2 Physical examination

A physical examination including weight and ECOG performance score will be performed at screening and at the time points specified in the Flow Chart. During the physical examination, the patient should be assessed for possible adverse events.

Boehringer Ingelheim BI Trial No.: 1270.1		04 Mar 201
01568809-08	Trial Protocol	Page 49 of 11

04 Mar 2015

#### 5.4 APPROPRIATENESS OF MEASUREMENTS

**Boehringer Ingelheim** 

Determination of MTD is based on toxicities graded according to CTCAE (R10-4848). The CTCAE criteria are commonly used in the assessment of adverse events in cancer patients.

The criteria to be used for evaluation of response  $(\underline{R10-4429})$  are well established and scientifically accepted.

**Trial Protocol** 

Page 51 of 111

Boehringer Ingelheim		04 Mar 2015
BI Trial No.: 1270.1 c01568809-08	Trial Protocol	Page 52 of 111
•		

Page 53 of 111

## 6. INVESTIGATIONAL PLAN

#### 6.1 **VISIT SCHEDULE**

During the treatment phase, after administration of BI 836826, patients are required to be hospitalized under close surveillance with access to intensive care for at least 48 hours after the second dose of BI 836826 in course 1 to allow close monitoring for infusion-related reactions, tumour lysis syndrome or other adverse events. After good tolerability of the first two doses in course 1 of BI 836826 the investigator may evaluate the risk for an infusion-related reaction and other adverse events in view of relevant comorbidities or CLL-related symptoms, and as a result, shorten the duration of surveillance to 24 hours.

**Trial Protocol** 

In case the patient demonstrated benefit after 4 treatment courses, and the investigator in agreement with the sponsor decided to administer 4 additional courses, the-decision whether to hospitalize the patient for application of courses 5-8 is left to the discretion of the investigator.

In case a patient misses a visit within one treatment course and the patient belatedly reports to the investigator between the missed and the next scheduled visit, the delayed visit should be scheduled as soon as possible and documented with the actual date and the reason for the delayed visit. The next visit, should still take place at the time it was originally scheduled in this treatment course.

However, in case the day of treatment administration (visit 1 of a course) is delayed, all subsequent visits of a course will be recalculated based on the actual date of visit 1 of the delayed course.

#### 6.2 DETAILS OF TRIAL PROCEDURES AT SELECTED VISITS

The investigations as outlined in the Flow Chart will be performed at the respective visits as described in detail in the following sections.

#### 6.2.1 Screening period

The screening period, i.e. the phase after informed consent and before the first administration of the trial drug, may be as long as 14 days.

The following parameters and investigations will be obtained and / or performed:

- Informed consent
- Demographics (sex, birth date, race)
- Medical history (oncological and relevant non-oncological)
- Review of inclusion and exclusion criteria (patient eligibility)
- 12-lead ECG
- Informed consent for pharmacogenetics
- Physical examination, body height, weight, vital signs and ECOG performance score

- Disease assessment:
- Safety laboratory (haematology, biochemistry including serum immunoglobulin levels and direct antiglobulin test, coagulation, urine; for details please refer to Section 5.2.3.1)

**Trial Protocol** 

- Serum pregnancy test in women of childbearing potential
- Virology screening (HBV, HCV, HIV, CMV) and CMV monitoring, for details refer to Section 5.2.3.3
- Dose assignment (during dose escalation phase only, before the first administration of the trial drug and after informed consent and review of in- and exclusion criteria)
- Concomitant therapy

### 6.2.2 Treatment periods

#### 6.2.2.1 Visit 1 - day 1 (day 1 of a treatment course)

On the treatment days, the following parameters and investigations will be obtained and / or performed:

- Review of inclusion and exclusion criteria (patient eligibility), in the first cycle only
- Blood samples for pharmacogenetic investigations (optional, only after signature of separate informed consent)
- Physical examination, weight
- Vital signs at time points specified in Section 5.2.5.1
- Adverse events (AEs)
- Changes in concomitant therapies
- Administration of BI 836826 after final confirmation of dose tier
- Safety lab parameters before trial drug administration as specified in Section 5.2.3.1
- •
- Blood samples to screen for evidence of tumour lysis syndrome (see Section 5.2.3.2)
- Serum pregnancy test in women of childbearing potential (does not have to be repeated in case pregnancy test has been performed within the last 3 days)
- CMV monitoring (see Section 5.2.3.3.2)

- •
- Response assessment (blood and clinical assessment) at the end of each treatment course prior to next administration of BI 836826, may be performed at day 1 of the next course prior to treatment administration or up to 1 day earlier to allow for a timely continuation of the treatment.
- Assessment of eligibility for further courses in all treatment courses except for course 1

#### 6.2.2.2 Visit 1 - day 2 (day 2 of a treatment course)

On the day after the treatment, the following parameters and investigations will be obtained/performed

- Administration of BI 836826 only in course 1
- Vital signs at time points specified in Section 5.2.5.1
- Adverse events
- Concomitant therapy
- Safety lab parameters as specified in Section 5.2.3.1
- Blood samples to screen for evidence of tumour lysis syndrome (see Section 5.2.3.2)
- •

#### 6.2.2.3 Visit 2 - day 3 (day 3 in course 1 or day 3 (+2) in course 2-8)

On visit 2, the following parameters and investigations will be obtained/performed

- Vital signs (see Section 5.2.5.1)
- Adverse events
- Concomitant therapy
- Safety lab parameters as specified in Section 5.2.3.1
- 6.2.2.4 Visit 2 day 4 (day 4 only in course 1)
- Vital signs (see Section 5.2.5.1)
- Adverse events
- Concomitant therapy
- Safety lab parameters as specified in Section 5.2.3.1
- •

6.2.2.5 Visit 3 - day 8 (day 8 in course 1 and day 8 (+2) in course 2-8)

On visit 3, the following parameters and investigations will be obtained/performed

- Administration of BI 836826 only in course 1, if treatment schedule according to Section 10.6 is used
- Vital signs (see Section 5.2.5.1)
- Adverse events
- Concomitant therapy
- Safety lab parameters as specified in Section 5.2.3.1
- Blood samples to screen for evidence of tumour lysis syndrome only in course 1, if treatment schedule according to section 10.6 is used
- - CMV monitoring (see Section 5.2.3.3.2)
- 6.2.2.6 Visit 3 day 9 (day 9 only in course 1, if treatment schedule according to Section 10.6 is used)

On visit 3, the following parameters and investigations will be obtained/performed

- Vital signs (see Section 5.2.5.1)
- Adverse events
- Concomitant therapy
- Safety lab parameters as specified in Section 5.2.3.1
- Blood samples to screen for evidence of tumour lysis syndrome
- •

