## 4. **TREATMENTS**

## 4.1 TREATMENTS TO BE ADMINISTERED

In course 1, the total dose will be divided into two portions administered on day 1 and 2 (please refer to the Flow Chart: Course 1, Dosing on Day 1 and Day 2).

The dose on day 1 will be 10% of the total dose, but not exceed 10 mg in case the total dose is higher than 100 mg. The dose on day 2 will be the planned total dose minus the dose administered on day 1. If adverse events which are related to the infusion schedule, e.g. infusion-related reactions or tumour lysis syndrome require administration of a lower dose on day 2, the total dose in course 1 may be divided into 3 smaller portions on day 1, 2 and 8. In this case, the dose on day 1 will remain as defined previously. The difference between day 1 and the planned total dose level will be equally divided between day 2 and 8 (reference to appendix 10.6). The distribution of the planned total dose in course 1 to two, or if needed to three smaller portions will be based on safety data from the previous cohort and will be assessed and may be modified by the DSMB. If supported by the DSMB, the same rules may be applied to course 2 in case infusion-related adverse events can be controlled by the above measures in course 1 but occur in course 2.

In all subsequent treatment courses, BI 836826 will be administered as a rate-controlled intravenous infusion on day 1 of each 14-day course.

The first and second infusion will be started at a rate of 10 mL/h. The infusion rate should be increased every 30 (+/-10) minutes by 10 mL/h to a maximum of 80 mL/h as long as tolerated by the patient. If considered safe by the investigator, the stepwise increase of infusion rate during the third and subsequent infusions may be faster or steps may be omitted, but the maximum infusion rate must not exceed 120 mL/h. If symptoms of an infusion related reaction occur, the infusion should be temporarily stopped. Upon recovery, it should be resumed at 50% of the rate at which the reaction occurred for at least 30 minutes. Lower rates may be selected if clinically indicated. Depending on the time of occurrence and the severity of the reaction, the investigator may consider administering additional supportive medication, e.g. corticosteroids. A stepwise re-increase of the infusion rate to a maximum of 80 mL/h is possible.

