#### 5.2.3.2 Screening for laboratory evidence of tumour lysis syndrome

Tumor lysis syndrome (TLS) is characterized by a group of metabolic derangements caused by the massive and abrupt release of cellular components into the blood after rapid lysis of malignant cells. The release of intracellular metabolites, including nucleic acids, proteins, phosphorus, and potassium, can overwhelm normal homeostatic mechanisms, potentially leading to hyperuricemia, hyperkalemia, hyperphosphatemia, hypocalcemia, and uremia. This can result in impaired renal function, and in some cases, in acute renal failure and even death (R10-4517). CTCAE classifies TLS in grade 3 (present), grade 4 (life threatening consequences; urgent intervention indicated) and grade 5 (death). Presence of TLS is not clearly defined by CTCAE (R10-4848). For this trial the Cairo-Bishop classification will be used to define presence of TLS, i.e. presence of clinical TLS (R10-4517).

To allow for early treatment in case TLS develops, vigilant monitoring is recommended. Between the first and the second infusion, during the first 48 hours after the start of the second infusion of BI 836826 in course 1 and during the first 24 hours after the start of the infusion(s) in course 2, in between timepoints at which a complete safety laboratory has to be performed, i.e. every 4-8 hours, the following laboratory parameters need to be determined to screen for evidence of a tumour lysis syndrome. In case the schedule as outlined in Section 10.6 is used, monitoring for TLS has to be performed for 24 hours also after the infusion on day 8.

Sampling for TLS in course 3 and subsequent courses should be performed as clinically indicated.

The actual date and time of the blood samples should be recorded in the eCRF.

Haematology	haemoglobin, haematocrit, red blood cell count (RBC), white blood cell count (WBC) with differential, platelets (PLT)
Biochemistry	uric acid, potassium, calcium, inorganic phosphate, lactate dehydrogenase (LDH), creatinine, urea

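### If course 2 is split over days 1, 2 and 8, as Protocol 4.1 permits, the visit lists and the Courses 2-8 chart contradict the tumour lysis monitoring that 5.2.3.2 requires

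*Protocol*

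**What the plan says.** **Dosing.** Protocol 4.1 splits the course 1 dose over days 1 and 2. If "infusion-related reactions or tumour lysis syndrome require administration of a lower dose on day 2", a three-portion split is allowed: the day 1 dose stays the same and the remainder is "equally divided between day 2 and 8 (reference to appendix 10.6"). The section then extends this: "If supported by the DSMB, the same rules may be applied to course 2", where infusion-related events are controlled by these measures in course 1 but occur in course 2.

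**TLS monitoring.** Section 5.2.3.2 requires a set of laboratory values every 4-8 hours, between the complete safety laboratories. For course 2 the period is "during the first 24 hours after the start of the infusion(s) in course 2". When the 10.6 schedule is used, "monitoring for TLS has to be performed for 24 hours also after the infusion on day 8". Only from course 3 does sampling become a matter of clinical indication.

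**Visit lists and charts.** For day 8, section 6.2.2.5 lists "Administration of BI 836826 only in course 1, if treatment schedule according to" 10.6 is used, and restricts TLS sampling in the same way: "Blood samples to screen for evidence of tumour lysis syndrome only in course 1, if treatment schedule according to" that section is used. Its title sets the timing as "day 8 in course 1 and day 8 (+2) in course 2-8". Section 6.2.2.6 provides a day 9 visit for course 1 only. Sections 4.1.3 and 6.2.2.2 also tie day 2 dosing to course 1. The Courses 2-8 chart marks drug on day 1 and TLS on days 1 and 2, and has no day 9 column. The 10.6 chart is headed for course 1 and then sends the reader to the Courses 2-8 chart.

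**The concern.** The option in 4.1 and the requirement in 5.2.3.2 fit together: the plural form used for course 2 infusions in 5.2.3.2 allows for a divided course. The visit-level text does not. For a three-portion course 2 it does more than stay silent, because its course 1 restriction contradicts 5.2.3.2.

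Sites usually work from the visit list and the chart. A site doing so in a divided course 2 could omit the repeated TLS samples after the day 8 dose and in the last hours after a day 2 dose. This is a first-in-human trial, TLS is a protocol-specified significant adverse event (5.2.2.1), and 5.2.3.2 gives early treatment as the purpose of the monitoring. A secondary effect is on reporting: SAP 5.4.5.2 derives laboratory TLS from values between 3 days before and 7 days after an administration, so each missed sample is one less chance of detecting it.

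**Working it through.** The plan states no figure to reproduce. The check compares the days on which 5.2.3.2 calls for TLS sampling with the days the schedule marks.

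**Inputs**
- Infusion days in a divided course 2: days 1 and 2, or days 1, 2 and 8 (4.1).
- Length of monitoring: 24 hours from the start of each infusion, at 4-8 hour spacing (5.2.3.2).
- Start time: any time of day (4.1.4).
- Marked TLS days: 1 and 2 (Courses 2-8 chart).

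**Step 1: days per infusion.** Twenty-four hours from a daytime start ends on the next calendar day, so each infusion needs sampling on its own day and the day after. The charts follow this pattern: the Courses 2-8 chart marks days 1-2 for a day 1 infusion, and the 10.6 chart marks days 8-9 for a day 8 infusion.

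**Step 2: compare.**

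| Course 2 schedule | Windows | Days needed | Marked | Unmarked |
|---|---|---|---|---|
| Two portions (days 1, 2) | 1-2, 2-3 | 1, 2, 3 | 1, 2 | 3 (1 of 3) |
| Three portions (days 1, 2, 8) | 1-2, 2-3, 8-9 | 1, 2, 3, 8, 9 | 1, 2 | 3, 8, 9 (3 of 5) |

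For reference, the 10.6 chart marks six TLS days for the same three-portion schedule in course 1: 1, 2, 3, 4, 8 and 9.

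**Step 3: samples at stake.** A 24-hour window at 4-8 hour spacing holds about 24/8 = 3 to 24/4 = 6 time points. The day 8-9 window is left out of the schedule entirely. Only the later part of the day 2-3 window is left out.

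**Step 4: what is still drawn.** The Courses 2-8 chart marks one general safety laboratory on day 3 (+2) and one on day 8 (+2). Under 5.2.3.1 it includes the TLS chemistry. Day 9 is therefore the only unmarked day with no scheduled blood draw. The day 8 window runs to day 10, whereas monitoring after a day 8 dose ends on day 9, so a late visit could fall outside it. The day 3 window raises the same problem.

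**Step 5: does another reading remove the conflict?** One could confine the day 8 sentence of 5.2.3.2 to course 1, because 10.6 is a course 1 chart. The separate requirement for course 2 infusions would still apply to a day 8 dose in course 2.

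**The case against.** The strongest answer is that the safeguard exists and binds. Section 5.2.3.2 makes the values mandatory in course 2, 4.1.4 requires all patients to be monitored and points to 5.2.3.2, and footnote 4 on the chart's TLS row does the same. Section 6.1 requires hospital surveillance after dosing, lets it be shortened to 24 hours after good tolerability in course 1, and leaves hospitalisation to the investigator's discretion only for courses 5-8. Course 2 therefore appears to stay under at least 24 hours of surveillance. All this stands, and it is why a site could, rather than would, miss samples. It does not remove the contradiction: footnote 4 belongs to a row left blank on days 3 and 8, and 6.2.2.5 restricts day 8 sampling to course 1.

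Three narrower points also have force.
- The stated trigger for dividing course 2 is infusion-related adverse events. TLS is named in the course 1 sentence, so one cannot say that these patients were selected for TLS risk.
- Section 6.2.2.3 lists no TLS sampling in course 1 either. There, however, the course 1 chart marks day 3; for course 2 neither list nor chart does.
- The +2 day window was written for undivided courses and does not move a dose that 4.1 places on day 8. It needs a clarifying phrase, no more.

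A reader might infer that a divided course 2 carries no TLS monitoring requirement, or that three of five days pass without any blood being drawn. The documents support neither, given 5.2.3.2 and the day 3 and day 8 safety laboratories. The course 1 dosing limits in 4.1.3 and 6.2.2.2 might also be taken to forbid dividing course 2. They do not: 4.1 can be read as the specific exception to that default.

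**Conclusion.** The inconsistency is real and should be corrected, because it sets a visit-level restriction against a mandatory safety measure. The main gap is the day 8-9 window of a three-portion course 2. The lesser gap is the day 3 end of the window after any day 2 dose in course 2. Counted in calendar days, 3 of 5 TLS days are unmarked with three portions and 1 of 3 with two. This rests on the pattern, also used in the charts, that a 24-hour window spans two calendar days.

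The reach is narrow: course 2 must be divided with DSMB support, and the main gap also needs the three-portion form. The documents give no frequency for this, so the number of patients affected is unknown. A reader might infer an effect on the dose-finding result, but there is none, because the MTD rests on DLTs in course 1.

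**What to change.** 1. In 6.2.2.5 (dosing and TLS sampling) and 6.2.2.6, change the restriction to *only in course 1, or in course 2 if divided under Section 4.1*. Put matching wording in 6.2.2.2 and 4.1.3 for consistency.
2. Add a footnote to the Courses 2-8 chart: in a divided course 2, TLS sampling per 5.2.3.2 continues for 24 hours after the start of each infusion (into day 3 after a day 2 dose; days 8 and 9 after a day 8 dose), with no +2 day window on those dosing and sampling days.
3. If 6.2.2.3 is edited, list TLS sampling per 5.2.3.2 there for course 1 as well as for a divided course 2, and add it for course 1 in 6.2.2.4. Naming only course 2 would suggest that course 1 needs no day 3 sampling, although the 48-hour rule applies there.

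Alternatively, if dividing course 2 is no longer intended, delete that sentence from 4.1. The choice lies with the sponsor and the DSMB.

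The cost is a few short wording changes and one footnote, plus a few extra samples and a day 9 visit for the few patients affected.

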#### 6.2.3.2 Follow-up

Follow-up visits will be performed after the EOT visit in case a patient has completed treatment according to protocol or is not eligible for further treatment courses prior to administration of the maximum number of courses. Follow up will end in case the patient is lost to follow-up, receives new anti-neoplastic therapy or in case the investigator and sponsor agree not to pursue further follow up visits. Follow-up visits should be performed at 4 weeks intervals or earlier if appropriate. Follow-up visits should be done at the investigational site, but may be performed by telephone interview in case the patient is unable to visit the investigator. Follow-up visits should be performed for 6 months after the EOT-visit. At the last follow-up visit, an end of trial assessment will be performed and documented in the eCRF. For follow-up of patients with adverse events which have not recovered at the last planned follow-up visit please refer to Section 5.2.2.2.

The following will be obtained and / or performed:

- Physical examination, vital signs and weight
- •
- Safety laboratory (haematology, biochemistry including serum immunoglobulin levels and direct antiglobulin test, coagulation, urine; for details please refer to Section 5.2.3.1)
- Response assessment (blood and clinical assessment)
- CMV monitoring (see Section 5.2.3.3.2)

Boehringer Ingelheim		04 Mar 2015
BI Trial No.: 1270.1		
c01568809-08	Trial Protocol	Page 59 of 111

- AEs since last visit in case they occurred during the observational period (6 weeks after the last trial drug administration) or are considered drug-related (see Section 5.2.1)
- concomitant therapy indicated for treatment of an AE
- Follow-up of AEs in case they were not yet recovered at EOT
- Outcome: date death (if applicable), date of progression (in case, the patient experienced PD)
- •

#### 6.2.3.3 End of the whole trial

The clinical trial will be analyzed and reported after the last patient has completed his / her last visit. In case the trial is ended by the sponsor when patients are still being treated with BI 836826 when the final report of the trial is being prepared, the patients will either be included in a follow-up trial or alternatively kept on treatment in this trial. Those patients will then be reported in a revised report and it will be noted in the original report that such a revised report will be written.

### 7. STATISTICAL METHODS AND DETERMINATION OF SAMPLE SIZE

#### 7.1 STATISTICAL DESIGN - MODEL

This trial will be performed as an open-label study. The primary objective of the trial is to determine the MTD of BI 836826. To determine the MTD, patients are entered sequentially into escalating dose tiers, initially in single patient cohorts and later on using the 3+3 design (see Section 4.1.4.). After the MTD has been determined, up to 30 patients are additionally entered at a dose level supposed to be recommended for Phase II.

#### 7.2 NULL AND ALTERNATIVE HYPOTHESES

The analyses in this trial are descriptive and exploratory. No formal statistical tests will be performed.

#### 7.3 PLANNED ANALYSES

#### 7.3.1 **Primary analyses**

The primary objective for this study is the tolerability and safety of BI 836826 as reflected by the MTD (for a definition of MTD, please refer to Section 3.1). In order to identify the MTD, the number of DLTs at each dose level must be presented. For the analysis of tolerability and safety, please refer to Section 7.3.3.

#### 7.3.2 Secondary analyses

#### 7.3.2.1 Number of lymphocytes in the peripheral blood

The number and the change of lymphocytes in the peripheral blood will be analysed descriptively by time point. The maximal reduction of lymphocytes with respect to all time points after baseline will be analysed.

#### 7.3.2.4 Blood counts

Blood counts will be analysed as part of the laboratory tests (see Section 7.3.3)

#### 7.3.2.5 Best overall response

Best overall response is the best response (CR, PR, SD or PD in this order) with respect to all time points. Remission rate is the rate of patients that either have CR or PR as best overall response. Best overall response and remission rate will be analysed descriptively. Frequency distributions and other descriptive statistical measures will be used to examine these variables.

These time-to-event variables will be analysed descriptively or with the Kaplan-Meier method if applicable. Details of censoring rules will be provided in the statistical analysis plan.

